| Window (days)      | ±7  |                            | ±7                         | ±7                         | ±7                          | ±7                          | ±7                          |                            | ±7                         | ±7                         | ±7                          | ±7                          | ±7                          | ±7                          | ±7                          | ±7                          | ±7                          | ±7                          | ±7                          | ±7        |   |    |    |   |   |   |   |   |   |   |   |                                 |  |  |                              |                              |
| Survival status    |   |                            |                            |                            |                             |                             |                             |                            |                            |                            |                             |                             |                             |                             |                             |                             |                             |                             |                             |           |   |    |    |   |   |   |   |   |   |   |   |                                 |  |  |                              |                              |

Abbreviations: AE = adverse event; BPI-SF = Brief Pain Inventory Short Form; CBC = complete blood count; CT = computed tomography; ECOG = Eastern Cooperative Oncology Group; EOT = end of treatment; ICF = informed consent form; IVRS / IWRS = interactive voice / web response system; MRI = magnetic resonance imaging; NCCN = National Comprehensive Cancer Network; PCWG2 = Prostate Cancer Clinical Trials Working Group 2; PRO = Patient-reported outcome; PS = performance status; PSA = prostate specific antigen; q6 = every 6; q12 = every 12; RECIST = Response Evaluation Criteria in Solid Tumors; SAE = serious adverse event; SSE = symptomatic skeletal event; US = United States; wk = week; WPS = worst pain score.

- a Once a subject switches from active follow-up with clinical visits to active follow-up without clinical visits, the subject will not be allowed to switch back. A subject with a possible SSE may, and is encouraged to, return to the clinic at any time to assess for the presence of an SSE.

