- b Once a separate, extended safety follow-up protocol, for the inclusion of subjects who received radium-223 dichloride in the course of Bayer sponsored clinical studies, has been implemented, the study subjects surviving after the end of the 2 years of active follow-up will be transitioned to this separate, extended safety follow-up protocol and the current study will be terminated at the time the last study subject is transitioned.
- c The maximum period for rescreening screen failed subjects is 35 days (14 days screening + 7-day window + 14 days for rescreening) from signing the ICF to randomization. Rescreening of a subject requires prior approval of the Bayer-designated medical representative (see Section 5.1). Eligibility should be confirmed within 14 ± 7 days of randomization.
- d The subject should return to the clinic in advance of the scheduled dose visit such that results of the laboratory assessment are available within 72 hours prior to dosing (each dose period is 28 ± 7 days after the prior dose of radium-223 dichloride).
- e Subjects who can no longer travel to the clinical site or who receive further anticancer therapy will only be followed up by telephone (active follow-up without clinic visits). Symptomatic skeletal events will not be collected over the phone.
- f The study record or subject's clinical record must clearly show that informed consent was obtained prior to any other study procedures being performed. Eligibility should be confirmed during the screening period and reconfirmed prior to dosing at Dose 1, Day 1.
- g Reconfirmation of eligibility and registration in the IVRS / IWRS: hematology results obtained within 72 hours of Dose 1, Day 1 should be reviewed and it should be confirmed that the values are still within the treatment ranges (absolute neutrophil count ≥ 1.5 x 10^9/L, platelet count ≥ 100 x 10^9/L, and hemoglobin ≥ 9.0 g/dL).

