during the active follow-up with clinic visits period. Contrast agents will only be captured as concomitant medication if there is an AE or SAE related to administration of contrast media.

- ee. Subjects who receive further anticancer therapy during the active follow-up period will have an end of active follow-up with clinic visits and will enter the active follow-up without clinic visits (telephone follow-up). Subjects who receive further anticancer therapy after 2 years from last study treatment will enter long-term follow-up.
- ff. All AEs and SAEs will be assessed and recorded from the time the ICF is signed until 30 days after the last dose of study medication. All AEs should be assessed and documented prior to each dose of radium-223 dichloride.
- gg. Any AEs and SAEs occurring beyond 30 days after the last treatment must be documented and reported if considered to be related to study medication or if related to an SSE. However, all occurrences of leukemia, myelodysplastic syndrome, aplastic anemia, and primary bone cancer or any other new primary malignancy must be reported as SAEs at any time and regardless of the investigator's causality assessment.
- hh. Any SAEs must be documented and reported if considered to be related to study medication. However, all occurrences of leukemia, myelodysplastic syndrome, aplastic anemia, and primary bone cancer or any other new primary malignancy must be reported as SAEs at any time and regardless of the investigator's causality assessment.

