**Active follow-up period *without* clinic visits:**

Subjects from the treatment period or the active follow-up period with clinic visits who can no longer travel to the clinical site will be followed for survival, treatment-related AEs and SAEs, SSEs, pain endpoints, and the initiation of other anti-cancer therapies with a phone call every 12 weeks ( $\pm$  7 days). In addition, subjects who receive cytotoxic chemotherapy will be followed up for the development of febrile neutropenia and hemorrhage during their chemotherapy treatment and for up to 6 months at a frequency based on local clinical practice. During this period, all occurrences of leukemia, myelodysplastic syndrome, aplastic anemia, and primary bone cancer or any other new primary malignancy must be reported as SAEs, regardless of the investigator's causality assessment.

The active follow-up period **without** clinic visits extends from the EOT period or the end of active follow-up with clinic visits until the subject experiences an SSE, dies, is lost to follow-up, or withdraws informed consent and actively objects to collection of further data.

The maximum duration of the active follow-up is 7 years from the last dose of radium-223 dichloride received by the subject.

All study subjects will be eligible for further follow-up either in this study or in a separate long-term follow-up study for up to 7 years. The separate long-term follow-up study has been set up to follow subjects who received radium-223 dichloride or placebo in the course of Bayer-sponsored clinical trials. The long-term follow-up study has a specific focus on investigator reported radium-223 dichloride-related AEs and SAEs, hematologic toxicity (e.g., myelosuppression / myelofibrosis / bone marrow aplasia), new primary malignancies, including leukemias and solid tumors, and survival for up to 7 years after last dose of radium-223 dichloride or until death. During long-term follow-

up, subjects will be contacted every 6 months by telephone. All subjects who transition into this separate long-term follow-up study will require a separate signed informed consent.

Transition of all subjects into the separate long-term follow-up study will begin following the later of primary endpoint completion or 2 years after the last radium-223 dichloride treatment is administered to the last treated subject.

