Subjects from the treatment period or the active follow-up period with clinic visits who can no longer travel to the clinical site will be followed for survival, treatment-related AEs and SAEs, SSEs, pain endpoints, and the initiation of other anti-cancer therapies (for prostate cancer, and cytotoxic chemotherapy and radiotherapy for any new malignancy) with a phone call every 12 weeks ( $\pm$  7 days). In addition, subjects who receive cytotoxic chemotherapy will be followed up for the development of febrile neutropenia and hemorrhage during their chemotherapy treatment and for up to 6 months at a frequency based on local clinical practice. During this period, all occurrences of leukemia, myelodysplastic syndrome, aplastic anemia, and primary bone cancer or any other new primary malignancy must be reported as SAEs, regardless of the investigator's causality assessment.

All study subjects will be eligible for further follow-up either in this study or in a separate long-term follow-up study for up to 7 years. The separate long-term follow-up study has been set up to follow subjects who received radium-223 dichloride or placebo in the course of Bayer-sponsored clinical trials. The long-term follow-up study has a specific focus on investigator reported radium-223 dichloride-related AEs and SAEs, all occurrences of leukemia, myelodysplastic syndrome, aplastic anemia, primary bone cancer or any other new primary malignancy, cancer treatment (including any systemic cytotoxic chemotherapy or radiotherapy for any malignancy; all systemic anti-cancer therapies for prostate cancer, including androgen synthesis inhibitors / androgen-receptor antagonists, systemic radioisotopes and radiation treatment; excluding analgesics), in subjects who receive cytotoxic chemotherapy: all occurrences of febrile neutropenia or hemorrhage during their chemotherapy treatment and for up to 6 months thereafter, and survival for up to 7 years after last dose of radium-223 dichloride or until death. During long-term follow-up, subjects, their treating health care professional, or caregiver will be contacted every 6 months by telephone. All subjects who transition into this separate long-term follow-up study will require a separate signed informed consent. Subject data collected at other standard-of-care visits and / or contacts may be used to satisfy study-required data.

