| Record chemotherapy for other malignancies               |   |                            |                            |                            |                             |                             |                             |                            |                            |                            |                             |                             |                             |                             |                             |                             |                             |                             |                             |                        | X   | X                    | X  | X                    | X   | X                          |
| Record radium-223 dichloride related AEs and SAEs gg |   |                            |                            |                            |                             |                             |                             |                            |                            |                            |                             |                             |                             |                             |                             |                             |                             |                             |                             |                        |   | X                    | X  | X                    | X   |                            |

b Subjects, their treating health care professional, or caregiver will be contacted every 6 months by telephone. Once a separate, extended safety follow-up protocol, for the inclusion of subjects who received radium-223 dichloride in the course of Bayer sponsored clinical studies, has been implemented, the study subjects surviving after the end of the 2 years of active follow-up will be transitioned to this separate, extended safety follow-up protocol and the current study will be terminated at the time the last study subject is transitioned. Subject data collected at other standard-of-care visits and / or contacts may be used to satisfy study-required data.

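### Scheduled SSE ascertainment ends on the move to telephone-only follow-up, Section 4.1 conflicts with Table 7-1 on this, and the loss can start about 24 weeks earlier in Arm A than in Arm C

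*Protocol*

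**What the plan says.** **Table 7-1 (Amendment 1, Change 26, new text).** Footnote e moves two groups to telephone contact: subjects who cannot travel and subjects on further anticancer therapy. They "will only be followed up by telephone (active follow-up without clinic visits). Symptomatic skeletal events will not be collected over the phone". Footnotes bb and cc add that SSEs are not identified or determined by telephone. The row for recording SSEs has no mark in the columns without clinic visits. Footnote a bars a return to scheduled clinic visits but leaves one route open: "A subject with a possible SSE may, and is encouraged to, return to the clinic at any time". Section 7.1.2.6 (Amendment 1, Change 12) requires an SSE found at an unscheduled visit to be recorded even under telephone-only follow-up.

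**Section 4.1 (Amendment 2, Change 10; Amendment 3, Changes 2 and 3).** Subjects "who can no longer travel to the clinical site will be followed for survival, treatment-related AEs and SAEs, SSEs, pain endpoints" and other items, with a call every 12 weeks. That period runs "until the subject experiences an SSE, dies, is lost to follow-up, or withdraws informed consent".

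**Therapy trigger.** Footnote ee reads "Subjects who receive further anticancer therapy during the active follow-up period will have an end of active follow-up with clinic visits", with no limit on the kind of therapy. Section 4.1 and Section 7.1.2.7.2 (Amendment 2, Change 32) give a closed list: cytotoxic chemotherapy for prostate cancer, other systemic radioisotopes, hemibody EBRT and other investigational drugs.

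**Leaving the study.** Under footnote b (Amendment 3), "the study subjects surviving after the end of the 2 years of active follow-up will be transitioned to this separate, extended safety follow-up protocol". Section 4.1 says "Transition of all subjects into the separate long-term follow-up study will begin following the later of primary endpoint completion" or 2 years after the last treated subject's last dose.

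**The concern.** SSE-FS needs SSEs and deaths to be sought with similar effort in every subject and arm for as long as the subject is at risk. Under footnote e the scheduled search for SSEs ends at the switch while survival follow-up goes on. The switch is also informative: it follows deteriorating health or a change of anticancer treatment, when an SSE may be more likely.

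Two consequences follow. First, sites have two incompatible instructions for subjects who cannot travel, so ascertainment may vary between sites. Second, in Comparison 2 (Arm A against Arm C from the 6th dose) the loss need not be balanced. Arm A subjects finish planned treatment first and can reach the therapy-driven switch while Arm C subjects are still seen at 4-weekly dosing visits. SSEs missed in the control arm make the control arm look better.

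**Working it through.** **1. The rules side by side.**

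| Question | Table 7-1 footnotes | Section 4.1 and related text |
|---|---|---|
| SSEs in subjects who cannot travel | Not collected by phone (e); clinic visit needed (a, bb) | Followed by 12-weekly call until an SSE |
| Therapy that ends clinic visits | Any further anticancer therapy (e, ee) | Closed list (4.1, 7.1.2.7.2) |
| Transition to the long-term study | After 2 years of active follow-up (b) | Later of primary endpoint completion or 2 years after the last subject's last dose |

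Section 7.5.1.3 (Amendment 2, Change 13) points the same way as footnote e: it limits reporting of SSE-related adverse events beyond 30 days to active follow-up with clinic visits. The long-term call list in Section 7.1.2.9.1 (Amendment 3) has survival but no SSE item.

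**2. Timing.** Table 7-1 puts the last planned dose at Week 20 (Arms A and B) and Week 44 (Arm C). The gap is 44 − 20 = 24 weeks. End of treatment is 30 days later: 20 + 30/7 = Week 24.3 and 44 + 30/7 = Week 48.3. Arms A and B share a schedule, so the timing argument concerns Comparison 2.

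**3. The plan's own power.** Section 8.6 gives 74.9 events, hazard ratio 0.606 (= 1/1.65), 1-sided alpha 0.10 and 80.6% power. By Schoenfeld with 1:1 allocation:

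power = Φ(√(74.9 × 0.25) × ln 1.65 − 1.282) = Φ(4.327 × 0.501 − 1.282) = Φ(0.885) = 81.2%.

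The stated figure reproduces.

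**4. Does the plan's simulation already allow for this?** A 9-month median gives exp(−(ln 2/9) × 5.52) = 0.654 event-free at 24 weeks (5.52 months). The stated proportion remaining is 0.5535. The implied loss rate is −ln(0.5535/0.654)/5.52, about 3.0% per month. Ordinary loss to follow-up is therefore allowed for. As described, loss of SSEs alone with deaths still counted is not.

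**5. Illustration.** From the plan: control hazard ln 2/9 per month, hazard ratio 0.606, 66 per arm (132.8/2), loss of 3.0% per month. Assumed: follow-up of 16 to 40 months; SSE share of the event hazard 50% or 90%; switching at 2%, 5% or 10% per month, from month 1 in Arm A and 24 weeks later in Arm C; 50% or 100% of later SSEs missed; deaths always counted. There were 3,000 trials per setting (2,000 for the no-loss reference), so simulation error is below 1 point.

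With no SSEs missed: power 82%, 79 events, hazard ratio 0.60.

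| SSE share | Switch per month | SSEs missed | Power | Mean hazard ratio | 1-sided rejection if true ratio is 1 |
|---|---|---|---|---|---|
| 50% | 2% | 50% | 77.7% | 0.62 | 8.4% |
| 50% | 5% | 50% | 74.6% | 0.63 | 7.2% |
| 50% | 10% | 100% | 60.6% | 0.69 | 2.8% |
| 90% | 2% | 50% | 73.0% | 0.64 | 6.1% |
| 90% | 5% | 100% | 43.5% | 0.75 | 1.8% |
| 90% | 10% | 100% | 25.2% | 0.85 | 0.5% |

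The six settings not shown lie inside this range.

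**6. Would waiting for the planned events repair it?** Put the diluted ratios into the formula in step 3 with 74.9 events. Ratio 0.618 gives Φ(4.327 × 0.481 − 1.282) = Φ(0.80), about 79%. Ratio 0.853 gives Φ(4.327 × 0.159 − 1.282) = Φ(−0.59), about 28%. Most of the loss is dilution of the effect, which extra follow-up to reach the event count does not restore.

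**The case against.** The strongest reply is that the protocol limits how an SSE is determined, not whether it is recorded. Telephone-only subjects are encouraged to return, and an SSE found at an unscheduled visit counts. That stands. A reader might infer from footnote e that SSE collection simply stops; the documents do not support this. The route is nevertheless least usable by subjects who are on the telephone because they cannot travel.

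Arms A and B also have SSE-risk calls at Weeks 28, 32, 40 and 44 and visits at Weeks 36 and 48. Section 7.1.2.7.1 (Amendment 2) asks early discontinuers to keep the Week 8 to 48 visits where possible. This partly offsets the 24-week gap. These provisions sit in the section on follow-up with clinic visits, and the text at hand does not say that they continue after a therapy-driven switch. Inability to travel can arise in any arm, including during treatment, so the timing argument applies only to therapy-driven switching. For that group, Section 4.1 agrees that clinic visits end and differs only on which therapies count.

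Amendment 4 asks for fractures and bone-associated events to be reported throughout follow-up regardless of causality. That may bring some skeletal events to light, but as adverse events; nothing at hand says they feed SSE-FS.

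The status of the text is a fair caution. Footnote e comes from the Amendment 1 new text. The logged changes to Table 7-1 in Amendments 2 and 3 do not alter it. The current table is not at hand, and the Amendment 4 wording is in a separate document.

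**Conclusion.** The inconsistency is real and bears on how a component of the primary endpoint is ascertained. Scheduled SSE ascertainment ends at the switch, capture becomes passive, and three sets of passages need reconciling: SSEs by telephone, the therapy trigger and the transition rule.

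If therapy-driven switching starts earlier in Arm A and SSEs are then missed, Comparison 2 is biased against extended dosing and its power falls below the stated 80.6%. Type I error is not inflated: in the simulation the 1-sided rejection rate under no effect falls from 10% to between 8.4% and 0.5%. The power range of about 78% to 25% rests on assumed SSE shares, switch rates and capture fractions, on deaths counting after the switch, and on no Arm C switching before its planned end of treatment. The actual size cannot be determined from the protocol.

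Some stronger readings are not supported. The pages at hand give no split of SSEs and deaths, so SSEs cannot be called the main component. A single figure such as 55% to 38% power needs 30% to 50% switching, a 60% SSE share and no SSE capture after the switch; censoring at the switch instead gives 74% to 66% on the same inputs. The protocol fixes none of these. Nor is there ground for claiming an arm-related timing bias in Comparison 1.

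**What to change.** Check footnote e against the current Table 7-1 and the Amendment 4 text. Then reconcile footnotes a, b, e, bb, cc and ee with Section 4.1 as follows.

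- **One ascertainment rule.** SSEs are sought for every randomized subject until death, withdrawal of consent or the primary cut-off, whatever further therapy is given and whichever follow-up mode applies. Screen at the existing 12-weekly call and confirm from a clinic assessment or treating-provider records.
- **One therapy trigger.** Use a single definition of the therapy that ends scheduled clinic visits in the footnotes, Section 4.1 and Section 7.1.2.7.2.
- **One transition rule.** Align footnote b with Section 4.1.

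Amendment 3 already introduces contact with the treating health care professional and lists Section 7.1.2.7.2 among the sections affected. The wording shown covers the six-monthly long-term calls, so it should be extended explicitly to SSE confirmation at the 12-weekly calls.

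The cost is protocol and CRF wording and some extra record retrieval. No new scheduled visits are needed.

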**Change 28:**

***Synopsis - Diagnosis and main criteria for inclusion:***

Paragraph 1, 7th bullet, item “g”:

Old text:

- g. Estimated glomerular filtration rate  $\geq 30$  mL/min/1.73 m^2 according to the Modification of Diet in Renal Disease abbreviated formula (~~Levey AS, et al. Ann Intern Med. 1999;130:461-70~~) (see Section 14.7)

Next text:

- g. Estimated glomerular filtration rate  $\geq 30$  mL/min/1.73 m^2 according to the Modification of Diet in Renal Disease abbreviated formula (24) (see Section 14.6)

***Synopsis - Plan for statistical analysis:***

Next to last paragraph:

Deleted text (correction of 1-sided alpha value):

Comparison 2 will be performed using a log-rank test with a 1-sided alpha of 0.1% stratified by the randomization factors (previous chemotherapy [ $\leq 1$  regimen versus  $> 1$  regimen] and total ALP [ $< 220$  U/L versus  $\geq 220$  U/L]). The extended dosing regimen will be declared superior to the standard dosing regimen if the 1-sided p-value from the stratified log rank test is less than 0.1%.

